#### 4. Study Procedures

- a. Study design, including the sequence and timing of study procedures (distinguish research procedures from those that are part of routine care).

This prospective randomized controlled study, will randomly assigned 200 participants into three groups: (1) *APA* (active points related to cLBP), (2) *Comparison Group (CG)-1* (non-active points, unrelated to cLBP), (3) *CG-2* (enhanced educational control, an educational booklet on cLBP will be given and the treatment used by participants for their cLBP will be recorded) (Fig. 1). Participants at CG-1 and CG-2 will have the opportunity to receive APA after completion of the study assessment. The EMA smartphone app will be used to collect real-time cLBP outcomes and adherence to APA practice. Treatment and nonspecific psychological placebo effects will be measured via questionnaires for all participants. Considering that the best evidence of the efficacy of acupuncture can last for 12 months after treatment, suggesting the potential APA effects, this proposed trial will evaluate the APA sustained effects for cLBP at 12-month follow-up. To avoid participant drop out, monthly phone follow-up will be used to collect study outcomes. Blood will be collected during office visits at baseline, post-APA treatment, and follow-up office visits at 1-, 3-, 6-, 9- and 12-months post-completion of treatment for a total of 7 assessments. Appointments will start between 9 and 11 am to control for circadian variation in cytokine levels. All proposed techniques have been established in our feasibility trial.

**Study Population:** Participants will comprise: (1) over 360 patients 65 years of age or older who are diagnosed with cLBP (March, 2017) in the Healthy Aging Studies Unit registry, (2) over 3,000 older adults yearly (from UTHealth), and (3) 3,900 from direct mailing (13,000 households of which 30% have cLBP). Given the diverse demographics of Houston (45% Hispanic, 23% African-American) and of outpatient visits at UTHealth clinics, we anticipate that we will recruit at least 35% minority participants. The male/female distribution corresponding to the most recent Houston, TX, census shows that females comprise 50.1% of the population, and males 49.9%.

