### c. Statistical plan including sample size justification and interim data analysis.

The primary outcomes are measured at 1-month post-completion of treatment. In our pilot study (i.e., pain intensity, pain interference, and physical function), Cohen's d (the effect sizes in terms of the standardized difference) ranged from 0.65 (physical function) to 1.28 (pain intensity) between the APA and the sham APA one month after intervention. Our pilot sham group (CG 1, non-reactive points) should have similar or better outcomes than CG 2 (enhanced usual care). The power calculation is based on the smallest observed effect size of 0.65 for a more conservative estimate for the sample size required in this proposed study to detect a difference between the active intervention and either of the control conditions. With 150 participants (50 participants in each of the three groups), we will be able to achieve 90% power to detect an effect size of .65 (between the APA and either of the CG arms) at a two-tailed significance level of 0.05. We anticipate that approximately 10% will be lost to follow-up at 1-month (primary endpoint) based on our pilot study (10% dropout at 1-month follow-up after 4-week APA), and [name] R01 (11% after 5 months follow-up). We plan to recruit 200 participants to allow for an adequate sample size in our exploratory analysis of the 12-month follow-up, assuming 25% of the enrolled sample will be lost to follow-up at 12-months. Achieving this sample size during a 42-months accrual period will require enrolling 58 participants per year, which should be feasible through our proposed recruitment strategies. With this sample size, we will be able to detect significant changes in some of the biomarkers (CGRP) but not all based on our pilot studies. We are collecting these to get a better estimate of the effect using a larger sample size.

Analysis plan for aim 1 will be to determine the efficacy of APA for cLBP at one month post treatment. For continuous outcomes, we will use a general linear mixed model (GLM) to construct a multilevel model for comparing the differences in the change in the outcomes from baseline to one month among the three groups. The group-by-time interaction is the main parameter of interest. This model will adjust for fixed

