effects from important demographic and clinical covariates, if needed. Random effects from subject heterogeneity and temporal autocorrelation with the first-order autoregressive (AR(1)) covariance structure will be used to model the repeated measurements. The comparison of all outcome measures between, before, and after APA will assess possible treatment placebos (i.e., point specificity) and blindness of intervention. In addition to reporting mean score changes of outcomes reaching clinical significance, a cut point of 30% improvement for primary outcomes will be used for responder analysis. For responder analysis of primary outcomes, we will adopt a generalized logistic mixed model with the same fixed and random effects and AR(1) covariance structure. In both models, violation of assumptions will be detected by corresponding model diagnostics. Using the approach outlined above, analyses will be conducted using the monthly data through 12 months to explore the maintenance of the effect over time. Quadratic terms will be included in the model to allow for non-linear change across time.

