Analysis for aim two, evaluating the effect of APA on biomarkers, the analytical strategies for Specific Aim 1 will be used. Outcomes at one-month post treatment will be examined using each biomarker individually and two latent variables with pre-defined biomarkers within the groups of pro- and anti-inflammatory biomarkers. We hypothesize that the analgesic effects of APA are the aggregating and counter-interacting effects of different biomarkers within each latent variable. Before analysis, we will check the normality assumption in original data and log-transformed data. If normality cannot be met in both types of data, we will use two alternative approaches: we will apply a non-parametric test (e.g., Kruskal-Wallis test) to do multiple comparisons in each time difference among three groups; We will categorize the change of biomarker measurement into increase (recoded as 1) and decrease (recoded as 0) from baseline, and apply a GLM, which can handle repeated measurements and subject heterogeneity. To examine the sustained effect of the intervention over time in biomarkers (baseline, 1, 3, 6, 9, 12 months), we will use the approach described in Aim 1 using linear mixed models with quadratic terms to model the change in biomarkers across time. Each biomarker will be tested individually and the two latent variable within pro- and anti-inflammatory biomarkers as well.

Aim three analyses will examine the moderating effects of demographics, comorbid conditions, treatment, and placebo effects, as well as the mediating effects of biomarkers in both primary and secondary outcomes. To examine whether or not demographics, comorbid conditions, and placebo effects moderate the relationship between APA treatment on primary and secondary outcomes, the previously described regression models in Specific Aim 1, which include the main effect terms for the intervention or group, will be

expanded to include the main effect terms for moderators and the three-way interaction terms between group, time, and moderators. Models will be simultaneously estimated under a framework of a mixed model structure by adding a covariance structure to consider possible correlations among biomarkers.

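### The group-by-time interaction, the only parameter Section 7c names for the exploratory 12-month maintenance analysis, does not test whether an effect remains at month 12

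*Combined protocol and SAP*

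**What the plan says.** Section 7c defines a mixed model for Aim 1 that compares the three groups on change between baseline and one month, and adds: "The group-by-time interaction is the main parameter of interest". The covariance is a random subject effect plus "temporal autocorrelation with the first-order autoregressive (AR(1)) covariance structure".

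For later follow-up the same section says that, by this same approach, "analyses will be conducted using the monthly data through 12 months to explore the maintenance of the effect over time". It continues: "Quadratic terms will be included in the model to allow for non-linear change across time". The Aim 2 paragraph takes the same route for the serum markers at baseline and months 1, 3, 6, 9 and 12, and gives its purpose as: "To examine the sustained effect of the intervention over time in biomarkers".

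On the status of the question, Section 2 and the sample-size paragraph of 7c treat the 12-month follow-up as exploratory. Section 4 is firmer: "this proposed trial will evaluate the APA sustained effects for cLBP at 12-month follow-up". Section 4 also contains a sample-size calculation that assumes 90% of the effect is kept at one year (0.585).

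Section 7c names no between-group contrast at month 12, no estimate of how much effect is retained, and no rule for calling an effect sustained.

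**The concern.** The question is whether four weeks of treatment still shows a benefit a year later. The one parameter that the plan names answers a different question: do the groups' curves differ anywhere between baseline and month 12? An effect present at month 1 makes the curves differ even if it then disappears. So the result the trial expects at its primary endpoint raises the chance of a significant 12-month interaction, whether or not anything remains.

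At stake is how the durability findings can be reported, for the clinical outcomes and for the biomarkers. Durability also carries weight in the design: 7c raises enrolment from 150 to 200 so that the 12-month analysis is adequately sized.

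**Working it through.** **1. The plan's own figure.** "The power calculation is based on the smallest observed effect size of 0.65", with two-sided 0.05 and 90% power. Per group, n = 2(1.960 + 1.282)² / 0.65² = 49.7, so 50. Power at 50 is Φ(0.65·√(50/2) − 1.960) = Φ(1.29) = 90%. Enrolment is 150 / 0.75 = 200. Both stated figures reproduce.

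**2. What the interaction tests.** Let δ(t) be the APA-minus-control difference at visit t, with δ(baseline) = 0 by randomisation.
- With baseline and month 1 only, the interaction is δ(1) − δ(baseline), which is the intended primary contrast.
- With all visits, the null is that δ(t) is the same at every t, hence zero throughout. Rejection says that δ(t) ≠ 0 somewhere. It does not say that δ(12) ≠ 0.

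**3. How often it is significant.** The test is a joint Wald test of group-by-time and group-by-time² in three arms (4 df). Power is P(χ²₄(λ) > 9.49), where λ = θ′Σ⁻¹θ, θ holds the expected interaction coefficients and Σ their GLS covariance.

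From the documents: 50 per arm, effect 0.65, quadratic time, random intercept plus AR(1).

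Assumed, because the documents do not give them:
- 14 visits: baseline, end of treatment, months 1-12
- total SD 1, both control groups flat
- effect 0.65 to month 1, then a linear fall to zero
- correlation at lag k equal to w + (1 − w)ρᵏ, with (w, ρ) = (0.3, 0.3), (0.5, 0.3), (0.6, 0.5), (0.5, 0.6), (0.4, 0.7), (0, 0.8)

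The 63-per-arm column uses the 270-participant text in Section 4: 90 × 0.7 = 63.

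| True course after month 1 | Effect at month 12 | Significant, 50 per arm | Significant, 63 per arm |
|---|---|---|---|
| gone by month 3 | 0 | 11-61% | 13-72% |
| gone by month 6 | 0 | 27-84% | 34-92% |
| gone by month 9 | 0 | 53-94% | 64-98% |
| fully sustained | 0.65 | 66-94% | 77-98% |

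At (0.5, 0.5) with 50 per arm, the test is significant in 58% of trials when the effect is gone by month 6, in 88% when it is sustained, and in 91% when it reaches zero exactly at month 12. The last two cases cannot be told apart by significance. A simulation with dropout from 67 to 50 per arm, at three of the covariances, gave 17-51% (gone by month 3), 40-72% (gone by month 6) and 4.6-5.4% under no effect at all.

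Making time categorical while keeping the overall test does not help. It is significant in 91-100% of trials when the effect has gone by month 3, 6 or 9.

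**4. A direct month-12 contrast, categorical visits.** Month 12 is 13 steps from baseline, so r = w + (1 − w)ρ¹³, the SD of change is √(2(1 − r)), and power is Φ(5 × effect/SD − 1.960), where 5 = √(50/2).
- (0.5, 0.5): r = 0.500, SD 1.000. Power is 90% for 0.65 and 83% for 0.585.
- (0.3, 0.7): r = 0.307, SD 1.177. Power is 79% for 0.65 and 70% for 0.585.
- (0.5, 0): r = 0.500, so the same as the first.
- Extremes of the six settings in step 3, for 0.65: (0, 0.8) has r = 0.055, SD 1.375, power 66%; (0.6, 0.5) has r = 0.600, SD 0.894, power 95%.

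With nothing left at month 12 it rejects 5% of the time.

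**5. The same contrast inside the quadratic model.** A quadratic cannot follow the jump between baseline and end of treatment, so it misfits baseline. At the three settings listed first in step 4, with the effect gone by month 6, the fitted change from baseline to month 12 is biased to between −0.24 and −0.56 SD. It rejects 19-99% of the time (58% at (0.5, 0.5); the top end is ρ = 0). With a constant 0.65 its power is only 51-58%.

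**6. Biomarkers.** With six visits, 50 per arm, the 0.40 effect mentioned in Section 4 and loss by month 6, the interaction is significant in 12-24% of trials at the same three settings. The fault is the same, but smaller.

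**The case against.** The strongest reply is that nothing in the plan says a significant overall interaction will be called a sustained effect. A reader might infer that a worn-off effect would be declared sustained, but the documents do not support this: the analysis is exploratory and has no decision rule. The fitted curve would also help a careful analyst. When the effect is gone by month 6, the quadratic model puts the month-12 group difference at −0.06 to −0.10 SD and finds it significant in 6-9% of trials. When 0.65 is held, the fitted difference is 0.57-0.61 SD. The approach being carried forward could also be read as the comparison of change from baseline, together with the mean changes and the 30% responder analysis. All of this stands. It limits the consequence, but it does not supply the missing month-12 parameter.

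Three stronger claims do not hold.
- A reader might infer that the test points the wrong way, because on follow-up visits alone a constant effect gives no interaction. But 7c models change from baseline and lists baseline among the biomarker visits.
- A rejection rate above 99% for loss by month 6 needs ρ = 0, whereas the plan specifies serial correlation.
- It is too strong to say that an early effect makes the interaction significant regardless. With loss by month 3 and strong serial correlation the figure is as low as 11%.

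For Aim 2, the non-parametric fallback already compares the groups at each time difference.

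**Conclusion.** The point holds as a gap between question and parameter. That the interaction tests equal trajectories follows from its definition and needs no assumption. The size does depend on assumptions: with 50 per arm and 0.65 at month 1, significance occurs in roughly 30-85% of trials when the effect has gone by month 6, about 10-60% if gone by month 3, and about 65-95% if fully sustained. These ranges rest on the assumed covariances, decay shapes and flat controls. They overlap so much that significance alone cannot support a claim of sustained benefit. The 1-month primary endpoint is untouched, because there the interaction is the right contrast. The plan should be corrected before the 12-month data are analysed, but this does not threaten the trial's main conclusion.

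**What to change.** In Section 7c, for the 12-month analysis of Aim 1 and likewise for the Aim 2 biomarkers:

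- Model time as categorical visits instead of linear plus quadratic. The quadratic must not be kept for the contrast below, because it biases the change from baseline.
- Name as the sustained-effect parameter the difference in change from baseline to month 12, APA minus CG-1 and APA minus CG-2, each with a 95% CI.
- Describe maintenance by the month-12 effect minus the month-1 effect, with its 95% CI.
- State that the overall group-by-time test is not evidence of a sustained effect.

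The cost is wording and a few contrast statements per outcome, with no new data or participants. The model has more parameters, and under some covariances the month-12 contrast has somewhat less power than a pooled trajectory test. The maintenance contrast will be descriptive. At (0.5, 0.5) the month-1 to month-12 correlation is 0.50, so its standard error is √(2/50 × 2 × 0.50) = 0.20 and the 95% half-width is 0.39 SD. Keeping 90% of the effect means a loss of only 0.065 SD.

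The contrast needs month-12 measurements. The Table 4 footnote, which stops monthly follow-up at 3 months, should be reconciled with the 12-month schedule elsewhere, as should the 200 and 270 enrolment figures.

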- **Specific Aim 1.** Determine the efficacy of APA for relieving cLBP at 1-month after completion of APA (primary endpoint) and explore monthly follow-up to 12-months to assess sustained effects of APA.

**Hypothesis a:** the APA group will experience significant improvement in cLBP primary outcomes (i.e., pain intensity, pain interference, and physical function) compared to the CGs. **Hypothesis b:** the APA group will experience significant improvement in cLBP secondary outcomes (i.e., lower analgesic use [the use of over-the-counter and prescription analgesics including opioids], quality of life, satisfaction, anxiety, depression, fear/avoidance, catastrophizing, improved relaxation, and sleep) compared to the CGs.

- **Specific Aim 2.** Determine the effects of APA on inflammatory signaling in cLBP. **Hypothesis:** APA will decrease circulating pro-inflammatory biomarkers (i.e., IL-1 $\beta$ , CGRP) and increase anti-inflammatory cytokines (i.e., IL-4) compared to the CGs.

- **Specific Aim 3.** Examine the relationship among potential mediators and moderators influence beneficial effects of APA on cLBP. **Hypothesis:** APA-induced cLBP symptom reduction will be mediated by changes in circulating inflammatory biomarkers and moderated by nonspecific placebo effects, relevant biological variables (e.g., age, gender, BMI), ethnicity, marital status, and comorbid conditions (e.g., smoking).

3. Background (briefly describe pre-clinical and clinical data, current experience with procedures, drug or device, and any other relevant information to justify the research)

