Appropriate model statistics (e.g., estimated regression coefficients [with 95% confidence intervals] for the interaction terms, change statistics based on likelihood ratio test, and F-statistics) will be used to evaluate moderation effects. Latent variable models will be used to examine the mediation effect of inflammatory biomarkers. Group assignment will be the independent variable and change in outcome from baseline to 1-month post treatment will be the dependent variable. Change in inflammatory biomarkers from baseline to immediately post-intervention will be included in the model as a mediator. The parameter of interest will be the indirect effect of treatment group through inflammatory biomarkers on change in outcomes.

d. Early stopping rules.

We do not expect any adverse events related to the testing procedures as they have no remarkable health risks. However, we will report all adverse events and evaluate on a case-by-case basis whether the occurrence of a particular adverse event has implications for discontinuing the study to ensure participant safety and well-being. Patients are allowed to drop out from the study if they do not feel comfortable with the procedures or they have an allergic reaction to the tape used for APA.

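### The Aim 3 moderation model does not name the moderator-by-time and moderator-by-group terms; fitted as written with reference or cell coding, a purely prognostic variable can be reported as a moderator of APA well above the 5% level

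*Combined protocol and SAP*

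**What the plan says.** Section 2 (Objectives, Specific Aim 3) hypothesises that the effect of APA is "moderated by nonspecific placebo effects, relevant biological variables (e.g., age, gender, BMI), ethnicity, marital status, and comorbid conditions (e.g., smoking").

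Section 7c builds the model for this in three steps.

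- **Aim 1 base model.** It compares change from baseline to one month among three groups: "The group-by-time interaction is the main parameter of interest". Covariates enter as fixed "effects from important demographic and clinical covariates, if needed"; no covariate-by-time term is mentioned.
- **Aim 3 expansion.** The Aim 1 models, "which include the main effect terms for the intervention or group", are to be "expanded to include the main effect terms for moderators and the three-way interaction terms between group, time, and moderators".
- **Decision statistics.** Moderation is evaluated with "estimated regression coefficients [with 95% confidence intervals] for the interaction terms, change statistics based on likelihood ratio test, and F-statistics".

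No section names a moderator-by-time or a moderator-by-group term. No section says how group and time will be coded.

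**The concern.** Moderation here means that the moderator's effect on change differs between arms. To isolate that, the model needs a separate term for the moderator's effect on change that is shared by all arms, which is moderator-by-time. If that term is absent, the shared effect has to go somewhere, and under common codings it goes into the three-way coefficients. The test then asks partly whether the variable predicts improvement at all.

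The three-group design is meant to address nonspecific influences such as beliefs and expectations. Such variables could plausibly predict improvement in every arm, though the documents give no data on this. If one of them does, Aim 3 could report that APA works differently by expectation or by age when the variable is only prognostic. The affected coefficients and tests are the ones the plan uses to judge moderation.

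**Working it through.** **The plan's own figures.** Section 7c states no power or error rate for moderation. Its sample-size figure reproduces: with 50 per arm and d = 0.65, 0.65 × √(50/2) = 3.25, and 3.25 − 1.96 = 1.29, which gives about 90% power. Also 150/(1 − 0.25) = 200.

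**Inputs from the documents.** Three arms, two visits (baseline and 1 month), two-sided 0.05, 200 enrolled, 10% lost by 1 month: 200 × 0.9/3 = 60 per arm.

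**Assumed inputs.** Standard normal moderator; outcome SD of 1 at each visit; baseline to 1-month correlation ρ = 0.5; the same slope b of change on the moderator in every arm, so no true moderation. With ρ = 0.5 the SD of change is √(2 × 0.5) = 1, so b is close to the moderator-change correlation (b = 0.3 gives 0.3/√1.09 = 0.29). With two visits, AR(1) and compound symmetry coincide.

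**Where the common effect goes (reference coding, CG-2 as reference).** The true moderator slopes are 0 at baseline and b at 1 month in all arms; a common baseline slope would change nothing. The written model allows slope m at baseline in all arms, m at 1 month in CG-2, and m + t at 1 month in APA and CG-1. The generalised least squares equations reduce to:

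- 6m + 2t = 3b
- (1 − ρ)m + t = b

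Hence m = b/(4 + 2ρ) and t = b[1 − (1 − ρ)/(4 + 2ρ)]. At ρ = 0.5, m = 0.2b and t = 0.9b. About 90% of a purely prognostic slope appears as an APA three-way coefficient whose true value is zero.

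**False-positive rate from the noncentral chi-square.**

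- Reference coding, 2 df: λ = n t²[2 − 2(1 − ρ)/3]/(1 − ρ²) = 60 × 0.81b² × 1.667/0.75 = 108b².
- Cell coding, where the three-way term takes 5 df and absorbs the two-way directions: λ = 3n b²/[2(1 − ρ)] = 180b².

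| b | Reference: λ, rate | Cell: λ, rate |
|---|---|---|
| 0.1 | 1.08, 14% | 1.8, 14-15% |
| 0.2 | 4.32, 44% | 7.2, 51% |
| 0.3 | 9.72, 80% | 16.2, 89% |

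**Simulation, same setting.** Across the two codings, simulated trials gave about 14-15%, 43-52% and 81-92% at correlations of 0.1, 0.2 and 0.3. A run of 1,000 trials per setting that estimated the covariance from the data gave somewhat lower figures: 13-15%, 42% and 75-77% with reference coding, and 14%, 49% and 88% with cell coding. With b = 0, all versions were near 5%.

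**Sensitivity.**

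- 50 per arm, reference coding, ρ = 0.5: 11-12%, 35-37% and 69-70% at b = 0.1, 0.2 and 0.3.
- 60 per arm, reference coding, ρ = 0.63: 18-19%, 58-59% and 88-90%.
- Section 4 also gives an enrolment target of 270 (90 per group). With 10% loss that is 90 × 0.9 = 81 per arm, and the two codings give 58-65% at 0.2 and 92-98% at 0.3. A larger trial makes the error more likely.
- Sum-to-zero group coding with centred time: about 6-8% in the 60-per-arm setting, and 4-9% over all settings run.

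**After the correction.** With all two-way terms, the three-way test rejected in 3.7% to 6.5% of trials in every setting. Adding moderator-by-time alone gave 4.0% to 6.2%, so that is the term that matters for the error rate.

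**The case against.** **The list may not be exhaustive.** The text says the models are expanded to include certain terms; it does not say only those. By ordinary convention an interaction carries its lower-order terms. The plan does not list a time main effect for Aim 1 either, yet any reader would assume one. This stands in part: the documents do not show that the sponsor has decided to leave the two-way terms out. But the sentence does spell out the moderator main effects, which makes silence on the two-way terms ambiguous. An analyst who follows it literally fits a model that does not test moderation, and one who adds the terms goes beyond the written plan.

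**The inflation depends on coding.** This is correct, and the plan gives no coding. Sum-to-zero coding with centred time nearly removes it. That protection requires building the product columns by hand. When the written model was entered as a formula with group and time as factors in one Python model-formula package (patsy), sum-to-zero contrasts still produced 12 columns and a 5-df term, which is the cell-coded case.

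**Cell coding already contains the full hierarchy.** True: only its 5-df omnibus test is mis-targeted, and the correct 2-df contrast can be drawn from the same fit. The plan does not say which of the two would be reported.

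**Some contrasts are safe.** With CG-2 as reference the bias enters APA and CG-1 equally, so APA versus CG-1 cancels (4.4-5.5% in simulation). With APA or CG-1 as reference that contrast is not protected.

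**The moderator strengths are assumed.** They are. Only a standard normal moderator was examined, although several named moderators are categorical.

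**Conclusion.** The concern holds as a gap in the specification that has a real consequence. Section 7c names moderator main effects and three-way terms but not the two-way terms involving the moderator. Under reference or cell coding, the resulting test can label a purely prognostic variable a moderator of APA well above 5%: about 14-15%, 43-52% and 81-92% at moderator-change correlations of 0.1, 0.2 and 0.3. These rates assume 60 per arm, a within-person correlation of 0.5 and a normally distributed moderator, and they illustrate the size of the problem rather than predict it.

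A reader might infer that every variable predicting improvement equally in all arms will be declared a moderator. That does not follow: weak predictors are flagged in a minority of trials, near-certainty needs a common slope of about 0.5 SD, and under sum-to-zero coding with centred time the rate is only about 6-8%. A reader might also infer that the efficacy result is at risk. It is not: the Aim 1 group-by-time test and its sample size do not involve the moderator terms. This is a should-fix.

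**What to change.** In the Aim 3 paragraph of Section 7c, state that each moderator model contains group, time, the moderator, all three two-way interactions among them (group-by-time, moderator-by-time, moderator-by-group) and group-by-time-by-moderator. State that moderation is judged only on the three-way term, which has 2 df for a continuous or binary moderator with two visits, followed by the APA versus CG-1 and APA versus CG-2 contrasts. For a moderator with more categories, the three-way term has 2 × (categories − 1) df. Once the hierarchy is complete, the three-way test no longer depends on how group and time are coded.

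The cost is one sentence and, for each continuous or binary moderator, three further coefficients (one for moderator-by-time, two for moderator-by-group), hence a small loss of degrees of freedom. No new data are needed and the sample size does not change.

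### The Aim 3 mediation model pre-specifies no covariates for the unrandomised biomarker-to-outcome path, so if APA shifts a biomarker, an indirect effect can appear without true mediation

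*Combined protocol and SAP*

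**What the plan says.** The mechanism claim is the Aim 3 hypothesis in section 2: "APA-induced cLBP symptom reduction will be mediated by changes in circulating inflammatory biomarkers". Section 7c gives the method at the end of the Aim 3 text. The model class is stated as "Latent variable models will be used to examine the mediation effect of inflammatory biomarkers". The variables are "Group assignment will be the independent variable and change in outcome from baseline to 1-month post treatment will be the dependent variable", followed by "Change in inflammatory biomarkers from baseline to immediately post-intervention will be included in the model as a mediator". The target is "The parameter of interest will be the indirect effect of treatment group through inflammatory biomarkers on change in outcomes".

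Covariates appear in two other places in section 7c:

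- The Aim 1 mixed model, which Aim 2 reuses, adjusts for "effects from important demographic and clinical covariates, if needed". None is named.
- For moderation under Aim 3, the Aim 1 models are "expanded to include the main effect terms for moderators and the three-way interaction terms between group, time, and moderators". The candidate moderators in section 2 include "relevant biological variables (e.g., age, gender, BMI), ethnicity, marital status, and comorbid conditions (e.g., smoking" and nonspecific placebo effects.

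The same Aim 3 text adds a covariance structure for correlation among the biomarkers. The plan does not state a no-confounding assumption for the mediation analysis, plan a sensitivity analysis for it, or name the test of the indirect effect.

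**The concern.** An indirect effect is the product of two paths: group to biomarker, and biomarker to outcome given group. Random allocation makes the first path causal. It does nothing for the second, because participants are not randomised to their biomarker change. Anything that moves both biomarker change and pain or function change within a group loads onto that second path.

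Correlated baselines are another route. If biomarker and pain are correlated at baseline and both regress towards their means, the two change scores are correlated even when neither affects the other.

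What is at stake is the interpretation of Aim 3. The neuro-immune pathway is a main part of the trial's rationale in sections 1 and 3. As the model is written, a significant indirect effect could not separate that pathway from shared causes.

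**Working it through.** **Does anything else supply the adjustment?** The Aim 1 covariates belong to a mixed model for repeated outcomes. The mediation text specifies a different model class and does not refer back to them. The moderation terms treat demographics and comorbidity as effect modifiers in the regression models, not as confounders in the mediation model. The covariance structure concerns correlation among biomarkers, not between biomarkers and pain. So no covariate is pre-specified for mediation.

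**The plan's own figure.** Section 7c states 90% power with 50 per group, effect size 0.65, two-sided 0.05. The normal formula gives Φ(0.65 × √(50/2) − 1.96) = Φ(1.29) = 0.901; the t-test gives 0.896. The figure reproduces, but it concerns Aim 1. No figure is given for mediation.

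**Inputs.**

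- n per group at 1 month: 200 × 0.90 / 3 = 60 (section 7c: 200 enrolled, 10% lost at 1 month). Section 4a also gives a target of 270, hence 270 × 0.90 / 3 = 81.
- Biomarker shift a: 0.40 SD is the detectable biomarker effect in section 4a. It is not an expected effect. 0.50 SD is an assumption.
- Residual within-group correlation r between biomarker change and outcome change: not in the documents. It is varied from 0 to 0.40.
- True biomarker-to-outcome effect: 0. Mediation is declared when both paths have p < 0.05 (joint-significance test, an assumption). The comparison is APA with one control, with a single observed biomarker standing in for the latent variable.

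**Formula.** The two path estimates are close to independent, so the false-mediation rate is about P(a) × P(b).

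- P(a) is the two-sample t-test power with 60 per group: 0.584 at a = 0.4 (normal check: Φ(0.4 × √30 − 1.96) = 0.591) and 0.775 at a = 0.5.
- P(b) is the power to detect a partial correlation r given group, with z = atanh(r) × √(120 − 4). At r = 0.20, z = 0.2027 × 10.77 = 2.18, so P(b) = Φ(2.18 − 1.96) ≈ 0.588.

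| r | P(b) | Product, a = 0.4 to 0.5 | Simulated |
|---|---|---|---|
| 0 | 0.050 | 2.9 to 3.9% | 3 to 4% |
| 0.05 | 0.084 | 4.9 to 6.5% | 5 to 7% |
| 0.10 | 0.191 | 11 to 15% | 11 to 14% |
| 0.20 | 0.588 | 34 to 46% | 34 to 47% |
| 0.40 | 0.995 | 58 to 77% | 58 to 78% |

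At 81 per group the simulated rates are about 6 to 21% for r = 0.05 to 0.10 and 52 to 90% for r = 0.20 to 0.40.

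**If APA does not shift the biomarker,** P(a) = 0.05, so the product cannot exceed about 5% whatever r is.

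**Size of the spurious effect.** With both changes scaled to SD 1, the false slope is about r, so the indirect effect is about a × r. That is 0.4 × 0.05 = 0.02 at the low end and 0.5 × 0.40 = 0.20 at the high end, or 3% to 31% of a 0.65 SD treatment effect.

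**Correlated baselines alone.** Let the baselines correlate at ρ, and assume a test-retest correlation φ = 0.5 for each measure with independent follow-up residuals. The change scores then correlate at (1 − φ)²ρ / [2(1 − φ)] = ρ/4. For ρ = 0.2 to 0.4 this is 0.05 to 0.10, which puts the false rate in the second and third rows of the table. Putting both baselines in both equations brought the simulated rate back to about 3 to 5%.

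**Effect of adjustment in general.** A three-arm simulation with one measured common cause, not affected by treatment, gave 2.7 to 5.8% once that cause was added, for every strength tried when APA shifted the biomarker.

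**The case against.** Several points on the other side carry weight.

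- **Silence is not exclusion.** The mediation text is a short summary. A reader might infer that the sponsor has decided on an unadjusted model; the documents do not say so. What stands is that no covariate is pre-specified, so the choice is open until the data have been seen.
- **Stable causes can cancel.** Age, BMI, smoking and comorbidity change little over two months. If they act additively and constantly on both levels, differencing removes them: in one check a level correlation of 0.36 gave a change-change correlation of 0.00. They confound only if they predict change in both measures. For the same reason, a reader might infer that change scores always add correlation through their baselines. That too is conditional: it requires correlated baselines and regression to the mean.
- **The high rates need strong confounding.** With a single shared cause, r = 0.20 to 0.40 means that it explains 20 to 40% of the variance of both changes. A reader might infer that a positive mediation result would usually be false. The documents give no correlation that supports this, and at r = 0.05 to 0.10 the rate is modest.
- **The bias needs a real biomarker shift.** Section 7c itself expects to detect changes in only some biomarkers. The condition is nevertheless the Aim 2 hypothesis, so it is the case the plan anticipates.
- **The time order is right.** The mediator is measured immediately after treatment and the outcome one month after treatment. This deserves credit, but it does not remove common causes.

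None of these supplies the missing adjustment. They limit the size of the problem, not its existence.

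**Conclusion.** The concern holds in conditional form. Followed as written, the plan leaves the biomarker-to-outcome path unadjusted. If APA shifts a biomarker, the indirect effect then mixes mediation with shared causes or baseline correlation. The false-mediation rate at 60 per group runs from near its no-confounding level to well over half, and the documents do not say where in that range the trial would fall. The direction of the argument follows from the model. The size rests on the assumed correlation, the assumed shift of 0.4 to 0.5 SD, the joint-significance test and a single observed biomarker.

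A reader might infer that the trial's efficacy conclusion is at risk. It is not: the mediation analysis belongs to Aim 3, and the Aim 1 comparison does not use it. The change is worth making before analysis, but it is not critical to the primary result.

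**What to change.** 1. In both the mediator and the outcome equations, pre-specify adjustment for baseline biomarker, baseline outcome, age, sex, BMI, smoking, comorbidity and baseline analgesic score. Baseline blood is planned in section 4a. Table 4 lists baseline outcomes, analgesic score, comorbidity and demographics. BMI and smoking are already needed for the Aim 3 moderation analysis.
2. State the assumption of no unmeasured confounding of biomarker change and outcome change.
3. Report a sensitivity analysis showing how much residual mediator-outcome correlation would reduce the indirect effect to zero.
4. State separately that analgesic use during treatment may itself be changed by APA, as the secondary hypothesis of Aim 1 expects. It should not be added as a simple covariate, and the analysis in item 3 does not cover it. Word the mediation conclusion with that limit.

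The cost is SAP wording, one extra sensitivity analysis and a more cautious mechanistic claim. No new data collection is needed.
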